ILIT dosing was performed every other week, rather than every four weeks. The authors found no significant differences in symptoms or QOL score. This result was discussed extensively in the literature (Hylander et al. 2013; Kündig et al. 2014; Malling et al, 2014) and speculated to be due to the frequency of injections. Kündig and colleagues noted that no FDA-approved vaccines are labeled with less than a 4-week interval between injections and that the Centers for Disease Control and Prevention (CDC) guidelines consider a vaccination “invalid” if the time interval is shortened to less than the recommended minimum. In fact, all other studies of ILIT in humans have chosen a 4-week time interval between injections in accordance with the general believe in vaccine immunology that the timing between inoculations is essential to allow phases in which little antigen is present in lymph follicles so that competition for the antigen can positively select high-affinity B cells memory B-cell formation and affinity maturation. Witten and colleagues did however observe significant improvement in chemical mediators, including an increase in IgG4 levels after treatment (for the x6 group:  $p = 0.0099$ , for the x3 group:  $p = 0.0128$ ). In addition, they found a 2.8-fold increase ( $p = 0.0005$ ) was seen in the x6 group and a 2.9-fold increase was seen in the x3 group for IgG4 levels, and levels of T cell cytokines were significantly lower IFN-gamma level in the x3 group relative to placebo with a tendency toward higher IL-10 levels indicating some modulation of the immune system in the treated patients.

In terms of safety and tolerability, the authors reported that the procedure was generally found tolerable, and only 1 patient withdrew because of discomfort during the examination. All adverse events during the study were mild with no moderate, severe, or life-threatening AEs reported, but most (83%) patients in the active treatment groups experienced some local, injection site discomfort or lymph node swelling. These authors emphasize that additional double-blind, placebo-controlled trials of ILIT are warranted and suggest that in accordance with FDA's Guidance for Industry and the World Allergy Organizations taskforce on AR that a composite symptom and medication score be the basis for efficacy assessments in future studies.

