#### Safety Endpoints:

1. Proportion of subjects experiencing a serious, treatment-emergent AE up to 60 minutes after the ILIT procedure.
2. Proportion of subjects experiencing systemic reactions to ILIT relative to placebo and severity of reactions relative to placebo as assessed by the Total Safety Score (TSS)
3. Proportion of subjects reporting local injection site reactions relative to placebo and severity of local reactions relative to placebo, as assessed by the TSS

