**14 APPENDIX 3 ASSESSMENT TOOLS AND RATING SCALES**

**Total Safety Score (TSS) Worksheet**

Subject ID:

Injection # (write in 1, 2, or 3):

RECORDING INSTRUCTIONS: Mark/code the box(es) indicating reactions experienced by this subject following injection (D = definitely related to study, P = probably related to study, N = not related to study)

ILIT protocol defined grading scale for severity# of adverse events			
	Mild	Moderate	Severe
LOCAL REACTIONS			
Lymph node swelling			
Itch			
Redness			
Other*			
SYSTEMIC REACTIONS			
Rhinorrhea			
Sneezing			
Dyspnea			
Cough			
Wheeze			
Pruritus			
Rash			
Angioedema			
Nausea			
Vomiting			
Diarrhea			
Headache			
Other*			

SCORING INSTUCTIONS: Give one score for most severe reaction (see scoring key on back) - min score 0, max score 4

SCORE for this injection	
---------------------------------	--

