**Total Safety Score Scoring Guide**

Safety Scoring Key	
Reaction	Point value
None	0
Local - if any marks in white boxes	1
Systemic mild (WAO Grade 1/2) - if any marks in green boxes	2
Systemic moderate (WAO Grade 3) - if any marks in yellow boxes	3
Systemic severe (WAO Grade 4) - if any marks in red boxes	4

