# Severity will be determined by study staff. Local reactions will be divided into: 1) mild: events require minimal or no treatment and do not interfere with the patient’s daily activities; 2) moderate: events result in a low level of inconvenience or concern with the therapeutic measures. Moderate events may cause some interference with functioning; 3) severe: events interrupt a patient’s usual daily activity and may require systemic drug therapy or other treatment. Severe events are usually incapacitating. Systemic reaction severity will be based on the World Allergy Organization grading for systemic allergic reactions (mild = grades 1/2, moderate = grade 3, severe = grade 4/5).

\*Will be specified if unexpected, unlisted reaction occurs.

Note: if epinephrine is used, the dose(s) will be recorded in the chart and CRF.

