2.3 Study Endpoints

The endpoints defined for this study are as follows:

Primary Efficacy Endpoint:

1. Average daily TCS during the 2018-2019 Mountain Cedar pollen season

Secondary Efficacy Endpoints:

Statistical Analysis Plan

1. Proportion of days during pollen season for which active patients experience a lower TCS than placebo patients
2. Patient reported pain or discomfort immediately after and 30 minutes post ILIT procedure
3. Patient-reported treatment satisfaction at the end of the study
4. Reduction in skin reactivity assessed using allergenic-specific serum IgE testing from pre-treatment to post-treatment (the end-of-study visit)

Exploratory Endpoints:

1. Use of rescue inhalers by patients with stable asthma

Safety Endpoints:

1. Proportion of subjects experiencing a serious, treatment-emergent AE up to 60 minutes after an intranodal injection procedure
2. Proportion of subjects experiencing systemic reactions to ILIT relative to placebo and severity of reactions relative to placebo as assessed by the Total Safety Score (TSS)
3. Proportion of subjects reporting local injection site reactions relative to placebo and severity of local reactions relative to placebo, as assessed by the TSS

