Local - if any marks in white boxes	1
Systemic mild (WAO Grade 1/2) - if any marks in green boxes	2
Systemic moderate (WAO Grade 3) - if any marks in yellow boxes	3
Systemic severe (WAO Grade 4) - if any marks in red boxes	4

Severity will be determined by study staff. Local reactions will be divided into: 1) mild: events require minimal or no treatment and do not interfere with the patient's daily activities; 2) moderate: events result in a low level of inconvenience or concern with the therapeutic measures. Moderate events may cause some interference with functioning; 3) severe: events interrupt a patient's usual daily activity and may require systemic drug therapy or other treatment. Severe events are usually incapacitating. Systemic reaction severity will be based on the World Allergy Organization grading for systemic allergic reactions (mild = grades 1/2, moderate = grade 3, severe = grade 4/5).

*Will be specified if unexpected, unlisted reaction occurs.

Statistical Analysis Plan

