10. SAFETY ANALYSIS

Safety analyses will compare treatment groups using appropriate methods according to their nominal or quantitative nature and will include descriptive statistics rather than formal hypothesis testing for noninferiority due to the small overall sample size. The study included a formal stopping rule in the event two systemic allergic reactions were detected.

The total safety score (TSS) and proportion of subjects with any treatment-emergent SAE, as defined in the composite safety endpoint, will be assessed using the Mann-Whitney test. Data will be presented in the form of descriptive statistics and appropriate tables and graphs with a conclusion on whether the significance level allowed the null hypothesis for each test to be rejected.

Safety Objective: To evaluate the safety profile of ILIT versus placebo using a standardized scoring system, the Total Safety Score worksheet, for AEs of interest (AEIs) up to 60 minutes post-procedure.

Statistical Analysis Plan

Safety Endpoints:

- Proportion of subjects experiencing a serious, treatment-emergent AE up to 60 minutes after an intranodal injection procedure
- Proportion of subjects experiencing systemic reactions to ILIT relative to placebo and severity of reactions relative to placebo as assessed by the Total Safety Score (TSS)
- Proportion of subjects reporting local injection site reactions relative to placebo and severity of local reactions relative to placebo, as assessed by the TSS

Additional safety tables and listings will include summaries of all patients experiencing anaphylaxis or treated with epinephrine, by group and a table of TSS reactions by severity by group.

Safety Population:

Safety analysis will include all participants who received at least one dose of study intervention regardless of whether they provided any diary data.

Calculation cumulative safety score (sum of TSS) across all patients by group will be performed in accordance with the scoring instruction described in section 7.4

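### The numeric Total Safety Score drops the grade of local reactions, so the score and its Mann-Whitney test cannot assess the severity half of safety endpoint 3, although the worksheet records those grades

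*Protocol*

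**What the plan says.** Safety endpoint 3 has two halves: how many patients have a local reaction, and how severe those reactions are. SAP 2.3 words it as "Proportion of subjects reporting local injection site reactions relative to placebo and severity of local reactions relative to placebo, as assessed by the TSS", and SAP 10 repeats it. Protocol 9.1 has the same severity clause: "severity of local reactions relative to placebo, as assessed by the TSS". Endpoint 2 asks the same two things of systemic reactions.

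The TSS is both a worksheet and a number.

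- **Worksheet** (Protocol Appendix 3, reproduced in SAP 7.4). Four local rows (lymph node swelling, itch, redness, other) and a separate block of systemic rows each have Mild, Moderate and Severe columns. The local grades have their own definitions: "Local reactions will be divided into: 1) mild: events require minimal or no treatment", and so on up to a severe grade for events that are typically incapacitating.
- **Number.** The instruction for each injection is "Give one score for most severe reaction (see scoring key on back) - min score 0, max score 4". The key gives 1 point for "Local - if any marks in white boxes", 2 points for "Systemic mild (WAO Grade 1/2) - if any marks in green boxes", and 3 and 4 points for moderate and severe systemic reactions. SAP 7.4 sums the visit scores for each patient.

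Protocol 9.4.4 and SAP 10 name the Mann-Whitney test for the TSS. SAP 10 also plans "a table of TSS reactions by severity by group". The endpoint table in Protocol section 3 describes the TSS differently, as a 0-to-4 rating of each local and systemic event of interest.

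**The concern.** The endpoint asks for a gradation that the score does not contain. An incapacitating local reaction and mild redness both receive 1 point. Because only the worst reaction per injection counts, a mild headache (a systemic row, score 2) removes a concurrent local reaction from the score altogether.

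Local reactions are the effect the protocol has most reason to expect. It cites a trial in which "most (83%) patients in the active treatment groups experienced some local, injection site discomfort or lymph node swelling". The worksheet is also the main record of reactions in the 60-minute observation period, because Protocol 8.3.3.1 and 8.3.8 keep worksheet events off the separate adverse event forms. SAP 10 promises a statement on whether each null hypothesis is rejected. For local severity, that statement would rest on a variable that cannot show a difference.

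**Working it through.** **Inputs.** The scoring rule and key are from Protocol Appendix 3 and SAP 7.4. The four local rows and three grades are from the worksheet. The group sizes of 12 v 11 and 16 v 16 reflect the 23 subjects and the maximum of 16 per group in SAP 5.1. One assumption is needed: that all local boxes are the white ones, since the colours are lost in the text. The key has no other category for local reactions.

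**1. The plan's own range.** No reaction scores 0; local only scores 1; systemic mild, moderate and severe score 2, 3 and 4. This reproduces the stated range of 0 to 4 per injection. Over three injections the maximum is 3 × 4 = 12.

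**2. Enumeration of local marks.** Four rows with four states each (none, mild, moderate, severe) give 4^4 = 256 patterns, of which 255 are non-empty.

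| Worst local grade | Patterns | Score, no systemic mark |
|---|---|---|
| Mild | 2^4 − 1 = 15 | 1 |
| Moderate | 3^4 − 2^4 = 65 | 1 |
| Severe | 4^4 − 3^4 = 175 | 1 |

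Scores 2, 3 and 4 each occur with no local mark and with every local grade. So the score also loses whether a local reaction occurred once any systemic box is marked.

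**3. The sum.** A cumulative score of 3 can arise as 1+1+1 (three local reactions of any grade), 2+1+0, or 3+0+0 (one moderate systemic reaction). The test ranks these patients equally.

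**4. Limiting case (invented data).** Every ILIT patient has a severe local reaction, every placebo patient a mild one, and nobody has a systemic reaction. The scores are all tied and Mann-Whitney gives p = 1. On the worksheet grades (3 v 1), p = 2.9 × 10^-8 at 16 v 16 and 3.2 × 10^-6 at 12 v 11 (normal approximation).

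**5. Simulated power, two assumed settings.** Three injections per patient, 3,000 trials per setting. The ranges cover repeated runs.

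- *A: equal frequency, different severity.* Of injections, 60% have a local reaction in both arms. Mild/moderate/severe is 33/33/33% on ILIT and about 83/13/3% on placebo.
- *B: different frequency, all mild.* Of injections, 60% on ILIT and 30% on placebo have a mild local reaction.

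| Setting | Per arm | Summed TSS | Worst local grade |
|---|---|---|---|
| A | 16 | about 5% | 84–86% |
| A | 12 | 4–5% | 72–75% |
| B | 16 | 82% | 50–51% |
| B | 12 | 69% | 36% |

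Setting A must return about alpha for the summed score, because that score ignores the only thing that differs. In setting B, worst grade reduces to any reaction at all: 1 − 0.4^3 = 0.936 against 1 − 0.7^3 = 0.657. It discards the number of injections that reacted, which the sum keeps (expected 3 × 0.6 = 1.8 against 3 × 0.3 = 0.9).

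**The case against.** A reader might infer that local severity cannot be measured with the TSS at all, or that endpoints 2 and 3 cannot be separated. The documents do not support either reading. Local and systemic reactions sit in separate blocks of the form, staff mark every reaction seen, and each local mark carries a defined grade. The proportion halves of both endpoints can be counted from those marks. SAP 10 treats the marks as TSS output by planning a severity table. Masking and tied sums affect the score, not the data. Nor would a related WAO grade 3 systemic reaction pass unnoticed because it ties with three local ones: Protocol 8.2 puts the study on hold for it.

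Three further arguments carry weight.

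- SAP 10 prefers description to formal non-inferiority testing because the trial is small, so endpoint 3 does not strictly need its own test. This stands, and any added comparison should be exploratory.
- The evidence cited in Protocol 2.2 points to differences in frequency more than in severity. The sentence containing the 83% figure says that all events were mild, and two other cited ILIT trials also report only mild reactions. Setting A is therefore not the expected case.
- Where all reactions are mild, replacing the summed TSS with worst local grade would lose power (setting B). It would also lose comparability with the cited US ILIT trial, which scored each injection 0 to 4 and summed. This rules out replacement.

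The severity table does not fully close the gap. It is not tied to endpoint 3. It does not say whether it counts patients, injections or marks, or whether severity means the local grades or the 0-to-4 key. The one named test still uses the score.

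**Conclusion.** The point holds as a gap in derivation, not as a missing measurement. The numeric TSS, and the Mann-Whitney test on it, cannot assess the severity half of safety endpoint 3, and a systemic mark hides a local reaction in the score. This follows from the scoring rule. It needs no assumption about event rates, only that all local boxes fall under the single local category of the key.

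The power figures are illustrative. The 5% against about 85% at 16 per arm depends on equal reaction rates and a large severity difference, both assumed. With mild reactions that differ only in frequency, the order reverses (82% against about 50%). Together the settings support adding a local-severity variable while keeping the summed score.

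**What to change.** In SAP 7.4 and 10:

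1. Derive endpoint 3 from the worksheet's local boxes, whether or not a systemic box is marked: the proportion of patients with any local reaction, and one named per-patient severity variable. Either worst local grade (0–3) over the three injections, or the worst local grade at each injection summed over the three, would serve. The second also keeps frequency: if all reactions are mild and none is systemic, it equals the summed TSS.
2. Derive endpoint 2 likewise from the systemic boxes: the proportion with any systemic reaction, and worst systemic grade.
3. Report these by arm, with an exploratory Mann-Whitney comparison of the severity variables, alongside the planned summed TSS.
4. State the unit of counting in the severity table and link it to endpoint 3.
5. Reconcile the Protocol section 3 description (each event rated 0 to 4) with the Appendix 3 rule (one score per injection).

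The cost is SAP wording and a few variables from boxes already collected. The downside is one or two more exploratory comparisons in a small trial.

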**Total Safety Score Scoring Guide**

Safety Scoring Key	
Reaction	Point value
None	0
Local - if any marks in white boxes	1
Systemic mild (WAO Grade 1/2) - if any marks in green boxes	2
Systemic moderate (WAO Grade 3) - if any marks in yellow boxes	3
Systemic severe (WAO Grade 4) - if any marks in red boxes	4

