### 6.2.4 PREPARATION

Preparation of syringes and, if necessary patient-specific extract dilutions will follow TASC's SOPs and the AAAAI Practice Management Resource Guide, 2014 edition, Allergen Immunotherapy Extract Preparation Manual. Specifically, bulk extracts will be diluted at the investigational drug pharmacy at a standard 1:100th dilution using Sterile Diluent for Allergenic Extracts. Dilutions will be made with sterile disposable syringes using aseptic technique using two sequential, 10-fold dilution processes to achieve the desired concentration for initiation and continuation of immunotherapy. For example, transferring 0.5 mL of a 10,000 PNU/mL extract into 4.5 mL of diluent will yield 5 mL of extract at 1,000 PNU/mL. For weight volume products, a 1:100 w/v dilution may be prepared from a 1:10 w/v by transferring 0.5 mL of the 1:10 w/v to 4.5 mL of diluent. Prepare as many additional serial dilutions as necessary to reach the appropriate concentration.

For patients that display a hypersensitivity reaction to the extract, as defined in section 5.2 (a wheal for allergenic extract greater than that for the positive control), the initial dose will be at an additional 1:10 dilution. For patients that experience a systemic reaction to any ILIT injection, as defined in section 2.3.2, subsequent ILIT injections will be made at a 1:10 dilution from the preceding treatment. Thus, the dosing will be as follows:

Baseline	Not Hypersensitive to Allergenic Extract on MQT				IS HYPERSENSITIVE to Allergenic Extract on MQT			
Injection 1	Inject 0.1 mL of undiluted IP				Inject 0.1 mL of 1:10 diluted IP			
Injection 2	No Systemic Reaction at Injection 1 Inject 0.1 mL of undiluted IP		SYSTEMIC REACTION at Injection 1 Inject 0.1 mL of 1:10 diluted IP		No Systemic Reaction at Injection 1 Inject 0.1 mL of 1:10 diluted IP		SYSTEMIC REACTION at Injection 1 Inject 0.1 mL of 1:100 diluted IP	

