## 8.3 ADVERSE EVENTS AND SERIOUS ADVERSE EVENTS

### 8.3.1 DEFINITION OF ADVERSE EVENTS (AE)

Any untoward medical occurrence in a clinical investigation subject administered immunotherapy or matched placebo which does not necessarily have a causal relationship with the treatment and is not otherwise related to their underlying medical condition or a comorbid condition present at the time of enrollment. An AE can therefore be any unfavorable and unintended sign, symptom, or disease temporally associated with the use of the immunotherapy or other medicinal product, whether or not related to the medicinal product, that has an onset after enrollment in the study and the initiation of treatment, defined as the injection of study treatment and the seven day period following. Events reported via the patient diary on the daily symptom score are by definition symptoms of the underlying disease and are therefore not adverse events. Symptoms may fluctuate and thus changes in symptoms are not considered adverse events but are rather measures of treatment efficacy for the underlying condition. Pre-planned procedures are not considered adverse events. Pre-existing conditions, unless worsened are not considered adverse events. Whenever possible, adverse events will be consolidated into the underlying diagnosis rather than a collection of separately reported symptoms, as determined by the investigator.

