7.4 Data Derivations

The following derivations will be made to produce analysis datasets.

- 1) Age at enrollment = Date of Enrollment – Date of birth
- 2) Total Combined Score: see below
- 3) Cumulative Safety Score: See below

Total Combined Score (TCS) is the sum of the daily symptom scores (DSS) and daily medication scores (DMS) for rhinoconjunctivitis. TCS will be calculated for each patient on each day that a diary result is available.

Daily Symptom Score (DSS) is derived from the patient diary according to the following rubric.

	no symptoms = 0	mild symptoms = 1	moderate symptoms = 2	severe symptoms = 3
1. runny nose				
2. stuffy nose				
3. sneezing				
4. itchy nose				
5. gritty/itchy eyes				
6. watery eyes				

Statistical Analysis Plan

Total DSS = Sum of individual symptoms scores.

Daily Medication Score (DMS) is derived from the patient diary according to the following rubric.

	No	Yes	
Did you use an oral antihistamine (Zyrtec) today?			If yes, score = 6
Dis you use antihistamine eye drops (olopatadine) today?			If yes, score = 6
Did you use a nasal corticosteroid (Flonase) today?			If yes, score = 8

Total DMS = Sum of scores for medical use reported on each day.

Thus, for each patient on each day during the allergy season is $TCS = DSS + DMS$. Since all patients were instructed to take a daily oral anti-histamine, the expected lower-bound for the TCS is a score of 6.

Total Safety Score – Each patient will receive a calculated Safety Score at each Treatment Visit (1, 2, and 3) based on the key below. A cumulative Safety Score for each patient will be calculated from the sum of the Safety Score at each visit. The Total Safety Score for a treatment group will be the sum of the cumulate Safety Score for each patient in the assigned group (ILIT or PBO).

Statistical Analysis Plan

Subject ID:

Injection # (write in 1, 2, or 3):

RECORDING INSTRUCTIONS: Mark/code the box(es) indicating reactions experienced by this subject following injection (D = definitely related to study, P = probably related to study, N = not related to study)

ILIT protocol defined grading scale for severity# of adverse events			
	Mild	Moderate	Severe
LOCAL REACTIONS			
Lymph node swelling			
Itch			
Redness			
Other*			
SYSTEMIC REACTIONS			
Rhinorrhea			
Sneezing			
Dyspnea			
Cough			
Wheeze			
Pruritus			
Rash			
Angioedema			
Nausea			
Vomiting			
Diarrhea			
Headache			
Other*			

Statistical Analysis Plan

Safety Scoring Key	
Reaction	Point value
None	0

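### The Total Safety Score key counts marks coded not related, and nothing on the worksheet separates continuing rhinitis from a reaction to the injection

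*Protocol*

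**What the plan says.** The worksheet in Protocol Appendix 3 instructs staff: "Mark/code the box(es) indicating reactions experienced by this subject following injection". Each mark carries one of three codes: "D = definitely related to study, P = probably related to study, N = not related to study". One score is then derived per injection: "Give one score for most severe reaction (see scoring key on back) - min score 0, max score 4". In the key, a local mark is worth 1 point, and the next level, worth 2 points, reads "Systemic mild (WAO Grade 1/2) - if any marks in green boxes". The systemic items include rhinorrhea, sneezing, cough, pruritus and headache.

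SAP 7.4 reproduces the key: "Each patient will receive a calculated Safety Score at each Treatment Visit (1, 2, and 3) based on the key below". The three visit scores are summed for each patient. Neither document adds a condition on the relatedness code or on symptoms already present.

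Safety endpoint 2 (Protocol 9.1, SAP 2.3) is the proportion with systemic reactions to ILIT, and their severity, as assessed by the TSS. Protocol 9.4.4 and SAP 10 compare the TSS by Mann-Whitney test.

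Two other passages bear on this. The study-hold rule in Protocol 8.2 does use relatedness when it refers to reactions on this worksheet. Protocol 8.3.1 states, for adverse events in general: "Pre-existing conditions, unless worsened are not considered adverse events".

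**The concern.** The endpoint is meant to measure reactions to the injection, but the key takes in symptoms that staff have judged unrelated. Several systemic items are also everyday symptoms of the disease under study. Rhinorrhea and sneezing appear on the diary's Daily Symptom Score too, and Protocol 8.3.1 treats symptoms reported there as disease, not adverse events.

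Background symptoms need not be absent at the treatment visits. SAP 6.4 expects some patients with other allergies, and Protocol 2.1 says that cedar also pollinates, less heavily, in November, while dosing starts around September and may last up to three months.

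Background marks raise the systemic rate in both arms and pull the arms together. In a safety comparison, a smaller difference between arms can hide a real excess.

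**Working it through.** **1. Does a not-related mark score?** The worksheet enters "N = not related to study" in the same boxes as the other two codes. The key asks only whether a box has any mark, and SAP 7.4 adds no filter. Taken as written, the answer is yes. A mild sneeze coded not related scores 2, and a definite local reaction scores 1. Because only the worst reaction counts, the sneeze also overrides the local reaction at that injection.

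**2. Can continuing symptoms be separated from new ones?** The schedule in Protocol 1.3 takes vital signs before injection and lists adverse-event and medication review at each treatment visit. Sections 8.1.1.3 and 8.1.1.4 repeat that review for the second and third injections. None of this records the worksheet symptoms item by item before the injection. A runny nose that continues afterwards is neither clearly included nor reliably excluded.

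**3. Size for the proportion with any systemic score.** The plan states no figure to reproduce, and no document gives a background rate, so b is an assumption. Let p be the true proportion with a systemic reaction over three injections. With b equal in both arms, independent of true reactions and independent across visits:

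observed proportion = 1 − (1 − p)(1 − b)³, so observed difference = true difference × (1 − b)³.

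If background symptoms always recur in the same patients (full clustering), the factor is (1 − b). With assumed true proportions of 25% (ILIT) and 5% (placebo):

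| b per injection | ILIT observed | Placebo observed | Difference, points | Share kept | Difference if fully clustered, points |
|---|---|---|---|---|---|
| 0 | 25.0% | 5.0% | 20.0 | 100% | 20 |
| 5% | 35.7% | 18.5% | 17.1 | 86% | 19 |
| 10% | 45.3% | 30.7% | 14.6 | 73% | 18 |
| 20% | 61.6% | 51.4% | 10.2 | 51% | 16 |

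At 16 per arm (the stated maximum) and two-sided 5%, approximate power under independence falls from 35% to 19%, 13% and 8%.

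**4. Size for the cumulative TSS.** Assume related mild systemic reactions at 10% versus 1.67% of injections and local reactions at 40% versus 15%. The expected score per injection is 2 − (1 − b)(1 − s)(2 − l), with s the systemic and l the local rate. The mean difference over three injections is therefore

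3(1 − b)[0.9833 × 1.85 − 0.90 × 1.60] = 1.137(1 − b),

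which is 1.14, 1.08, 1.02 and 0.91 at b = 0, 5, 10 and 20%. A simulation with 16 per arm and 4,000 runs gave 1.13, 1.09, 1.02 and 0.92, with Mann-Whitney power of 0.875, 0.745, 0.605 and 0.413.

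**5. Indirect evidence on b.** Protocol 2.2 describes an earlier US intralymphatic trial that used a TSS. It had 15 patients with three injections each (45 injections), and only localised reactions are described. Zero systemic events in 45 gives a one-sided 95% upper bound of 1 − 0.05^(1/45) = 6.4%. At that bound (1 − 0.064)³ = 0.82, so about 16.4 of 20 points remain. How that trial handled unrelated symptoms is not stated.

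**The case against.** A reader might infer that the TSS counts rhinitis already present before the injection. The documents do not say so. The worksheet is limited to what follows the injection, and systemic severity uses a grading scale for allergic reactions. The worksheet items are also called adverse events (Protocol 8.3.3.1, 8.3.8), so the exclusion of unworsened pre-existing conditions can be read as applying to them. That stands. What is missing is a record and a written rule that would make the exclusion work.

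A reader might also infer that ordinary rhinitis would cause later injections to be diluted. Section 6.2.4 is worded causally: "For patients that experience a systemic reaction to any ILIT injection, as defined in section 2.3.2". It refers to neither the score nor worksheet marks, so this consequence is not shown. The section it cites covers benefits and contains no such definition, so the cross-reference is a defect in its own right.

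Background may also be low. Protocol 2.3.1 advises against starting immunotherapy during exposure symptoms and addresses withholding or lowering a dose for severe rhinitis. Together with the 6.4% bound, this makes the upper rows of the table less likely. It does not exclude mild symptoms at the second or third injection.

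Finally, scoring events of any cause is defensible. Protocol 8.3.3.2 says the product must always be suspected, and 8.3.4 documents adverse events whatever their relationship. Dropping unrelated marks also makes the score depend on staff judgement. This is a good reason to keep an all-marks analysis. It does not fit an endpoint defined as reactions to ILIT, nor the relatedness condition in 8.2.

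**Conclusion.** The point holds in a limited form. As written, a mark coded not related earns the same TSS points as a definite reaction, and this needs no assumption. Whether continuing background symptoms also enter the score is left open by the plan.

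The numerical effect rests on an assumed b, on equal background in both arms, and on independence from true reactions and across visits. A 20-point difference becomes about 17 points at b = 5%, 14.6 at 10% and 10.2 at 20%. Clustering within patients reduces the loss, and the indirect evidence points to the low end.

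The effect is confined to safety endpoint 2 and the Mann-Whitney test of the TSS. A reader might extend it to all safety results, but the primary composite (anaphylaxis, epinephrine, other serious events) does not use the score, and rhinitis marks create no local reactions for endpoint 3. The direction is also not simply favourable to the product: the difference between arms shrinks while the absolute rate in each arm rises. SAP 10 describes safety as descriptive because of the small sample, which lowers the stakes, but it keeps the tests.

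**What to change.** In Protocol Appendix 3 and SAP 7.4, base the TSS on symptoms coded definitely or probably related that are new or worse than before the injection. Add a pre-injection column with the same symptom list to the worksheet. Report the all-marks score as a sensitivity analysis and list the marks coded not related.

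The relatedness part needs no new data, because the codes are already collected; it should be settled before unblinding. The pre-injection column helps only for injections not yet given, and the SAP describes enrolment and treatment in the past tense. Where the column cannot be added, the report should say that continuing symptoms could not be separated. The cost is about a minute per visit and some reliance on blinded relatedness coding.

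Two items need reconciling. The worksheet codes are definitely, probably and not related, whereas Protocol 8.2 speaks of possibly or definitely related. The term systemic reaction in 6.2.4 is referred to 2.3.2, which does not define it; those passages and the worksheet must be brought into agreement.
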